6. STATISTICS AND DATA ANALYSIS
7. REGULATORY ISSUES
8. STUDY MANAGEMENT
9. PUBLICATION POLICY
10. REFERENCES

1. STUDY SUMMARY

- AIM** To evaluate the effects of increased intakes of citrus fruits and cruciferous vegetables on vascular function in untreated, prehypertensive participants
- DESIGN** Randomised controlled, cross-over trial with three 14-day dietary intervention periods, preceded by one week run-in period and separated by one week wash-out periods, 9 weeks in total. The diet will be fully controlled and provided by the researchers. Participants will receive in random order three interventions:
- 1: 1 portion of fruits plus 1 portion of vegetables, of commonly consumed types per day. Intakes are at 25th percentile of UK consumption and will exclude citrus fruits, cruciferous and allium vegetables.
 - 2: 4 portions of fruits plus 4 portions of vegetables, of commonly consumed types per day excluding citrus fruits, cruciferous and allium vegetables.
 - 3: 4 portions of citrus fruits plus 4 portions of cruciferous vegetables per day.
- Numbers of fruit and vegetable portions for the treatment groups are according to recommendations of the Dietary Approach to Stop Hypertension (DASH) diet.¹ Diet and macronutrient balance will be based on UK average habitual diet (NDNS). Body weight will be maintained by tailoring the diet to individual energy requirements.
- POPULATION** 36 apparently healthy men and women, aged 40 to 65 years, with upper levels of prehypertension (systolic BP 125-160 mmHg), not using antihypertensive, other cardiovascular, or diabetic medication, with a body mass index between 20 and 35 kg/m², with a habitual dietary pattern low in plant foods (≤ 4.2 portions per day) and with sufficient available food storage at home will be recruited.
- Exclusion criteria include smoking, pre-existing morbidity including diabetes mellitus, hypertension, cardiovascular or other metabolic diseases, ≥ 10 hours per week of moderate to vigorous physical activity, excessive habitual alcohol intake of >21 units per week (females) or >28 units per week, adherence to a prescribed diet, pregnancy or lactation, use of dietary supplements, food sensitivities, or vegetarian/vegan diet by choice.
- TREATMENT** **7-day run-in/washout periods:** Participants will be asked to consume the run-in or washout (control) diet for 7 days. A run-in period is to minimize the effect of habitual diet intake before start of intervention, a washout period is to ensure that potential cardiometabolic effect of the previous intervention diet is eliminated.
- 14-day dietary intervention periods:** Participants will consume the control or intervention diet, weekly delivered at their home. Participants will be asked to visit the Cambridge Epidemiology & Clinical Trials Unit testing sites 7 times in total (every 1st and 15th day of each intervention sequence) in fasted condition.
- Day 1 and day 15 of 14-day dietary intervention periods:** Participants will be asked to arrive in fasted condition and stay at the testing site until the last measurement has been completed. Participants will bring 24-hr urine and stool collections. The following measurements will be done: anthropometrics, bioelectrical impedance, blood pressure,

pulse wave velocity, and cognitive function. Samples of fasting blood will be taken. Participants will complete questionnaires to assess maintenance of lifestyle factors e.g. physical activity and appetite profiles throughout the study. Breakfast will be provided.

DURATION Participants will be involved for 9 weeks in total:

Week 1: Run-in period

Week 2-3: 14-day dietary intervention

Week 4: Wash-out period

Week 5-6: 14-day dietary intervention

Week 7: Wash-out period

Week 8-9: 14-day dietary intervention

OUTCOME MEASURES

Primary outcome: Changes in systolic and diastolic blood pressure (mmHg)

Secondary outcomes: Changes in:

- Arterial stiffness assessed by pulse wave velocity and pulse wave analysis
- Cardiovascular risk factors measured in fasted blood samples
- Markers of endothelial function measured in fasted blood samples
- Markers of low-grade inflammation measured in fasted blood samples
- Urinary and circulatory metabolite profiles and individual metabolite levels
- Established objective urinary and circulatory markers of intakes of fruits, vegetables, and other foods
- Composition of gut microbiota
- Cognitive function
- Average total, daytime, night time 24-hr ambulatory blood pressure (in subsample)
- Average objective physical activity intensity and sleep time (in subsample)

2. INTRODUCTION

2.1 Background

Elevated blood pressure (BP) is a leading population-wide modifiable risk factor of cardiovascular diseases (CVD), which contributes yearly to ~31% of all deaths globally.² Hypertension ($\geq 140/90$ mmHg^{3,4}) is prevalent in 40% of adults, while a billion of individuals have prehypertension (120-139/80-89 mmHg³) and are at higher risk to develop hypertension and CVD. The strong, well-established evidence on the adverse relationship between higher BP and risk of CVD events emphasizes the need for targeted, practical lifestyle modifications to maintain healthy BP levels to prevent future CVD events.

2.2 Rationale of current study

Low fruit and vegetable consumption have been identified as major risk factors contributing to hypertension and CVD. Meta-analyses of prospective cohort studies showed strong evidence that eating higher amounts of fruit and vegetables lowers the risk of CVD by ~20% in a dose-response manner.⁵⁻⁸ Two landmark large intervention studies demonstrated that untreated mildly hypertensive participants who increased their daily fruit and vegetable intakes significantly reduced their average systolic BP by 2.8 mmHg systolic and diastolic by 1.1 mmHg compared to the control group with average US diet, with stronger BP-lowering effects in hypertensive participants.^{1,9} These findings underlie the evidence of the current dietary recommendations to eat at least 5 (80 gram) portions of a variety of fruits and vegetables per day with a limit of 150 ml 100% pure, unsweetened juice counting as one portion.

Fruits and vegetables are however biologically and chemically complex and vary largely in amounts and types of nutrients and bioactive compounds. Prospective cohort studies have only since 2010 started to investigate the influence of eating higher amount of specific types of fruits and vegetables on the risk of CVD. Meta-analyses of prospective cohort studies indicate that higher intakes of apples and pears, citrus fruits, carrots, cruciferous vegetables (e.g. broccoli and cabbage), grapes, green leafy vegetables, raw vegetables, and tomatoes have been suggested to lower the risk of CVD by 14-22%.⁸ Few cross-sectional¹⁰ and prospective cohort studies^{11,12} have been published on associations of types of fruits and vegetables with BP or risk of hypertension, with inconsistent findings.

Subsequent dietary intervention studies attempted to demonstrate BP-lowering effects of specific types of fruit and vegetables, but with inconsistent findings. So far, interventions have been mainly focused on fruits and vegetables abundant in a single nutrient e.g., flavonoids¹³, lycopene¹⁴, potassium¹⁵, or nitrate¹⁶. Acknowledging the complexity of foods, we have only recently understood that we need to look at whole foods as the constituents act in combination and in synergy on health.¹⁷ Only by investigating the whole food will improve our understanding of potential synergistic and underlying mechanisms of BP-lowering effects of specific types of fruits and vegetables, which can be used to develop understandable, targeted dietary strategies to lower BP at a population-wide level.

The main limitation of nutritional research is the use of traditional, self-reported dietary assessment methods with high prevalence of misreport leading to over- or underestimation of dietary intakes and associations and thus misinterpretation of findings. Established biomarkers to assess fruit and vegetable intakes include urinary potassium and plasma carotenoids, flavonoids, and vitamin C. These biomarkers measure intakes of nutrients from various dietary sources and are nowadays often supplemented to foods, which may overestimate calculation of fruit and vegetable consumption. A new approach is metabolomic profiling of biofluids using Nuclear Magnetic Resonance (NMR) spectroscopy and/or mass spectrometry (MS) to measure many small compounds in biological fluids (urine and blood) simultaneously. Recent advances demonstrated that metabolomic strategies can be used to develop objective biomarkers of dietary intake¹⁸ and at once comprehensively characterises diet-related metabolic responses in human biofluids.¹⁹ Urinary biomarkers reflect the end product of metabolism. Urinary biomarkers combined with

assessment of compounds in food, blood (controlled to maintain homeostasis), and changes in gut microbial composition will provide a systematic approach to aid identification of underlying mechanisms of fruit and vegetable-induced BP effects.

Using metabolomic strategies, small, short-term intervention studies have identified potential biomarkers for citrus fruits (proline betaine) and broccoli (S-methyl-L-cysteine sulfoxide (SMSCO)) in healthy participants.^{20,21} In a large-scale epidemiologic cohort study, the PI investigated their validity by combined analyses from high quality dietary data (24-hour dietary recalls), measured BP data and 24-hr urine collections measured by NMR spectroscopy from 2,032 US and 449 UK participants. In both populations and across clinic visits, consistent and strong correlations were found for intakes of citrus fruit with proline betaine (0.72), 4-hydroxyproline betaine (0.63) and several co-metabolites (0.22-0.49) related to the same metabolic pathway and for cruciferous vegetables with S-methyl-L-cysteine sulfoxide (SMSCO, 0.39). These biomarkers will be highly valuable as objective assessment of citrus fruits and cruciferous vegetable intake, as unbiased estimates of associations with disease outcomes in large-scale epidemiological studies, and as objective measures of compliance in intervention studies.

Although meta-analyses of prospective cohort studies indicate that higher intakes of citrus fruits and cruciferous vegetables lower the risk of CVD⁸, limited evidence exists from intervention studies. Few small, acute interventions showed inconsistent findings on BP and endothelial function after supplementation of flavanones and/or orange juice²⁵⁻²⁷, while little evidence exists on cardioprotective effects of cruciferous vegetables.²⁸⁻³⁰ Based on the evidence from prospective cohort studies and recent identification of strong, specific, and validated urinary markers for these metabolites, we will test increased intakes of citrus fruits and cruciferous vegetables on vascular function in this intervention study as proof of concept to develop future, larger intervention studies. We will not only test increased intakes of citrus fruit and cruciferous vegetables against low fruit and vegetable consumption, but also against increased intakes of other fruits and vegetables to rule out the effect of the higher amount consumed.

In this pilot study, we will take into account the complexity of the whole food and will test the effects of higher intakes of citrus fruits and cruciferous vegetables on vascular function and cardiometabolic risk factors using predefined novel biomarkers to measure compliance. The simultaneous approach of measuring metabolites in various biofluids enables us to further validate these biomarkers and to assess changes with other urinary and circulatory metabolites to improve our understanding of potential underlying mechanisms and pathways. Additionally, we will also test cognitive function reported to relate to improved blood flow and neural activity following higher fruits and vegetable intakes.

3. STUDY DESIGN

This is a fully controlled randomised cross-over trial with three 14-day dietary intervention periods, preceded by one week run-in period and separated by one week wash-out periods, 9 weeks in total, in 36 apparently healthy, untreated, prehypertensive participants aged between 40 and 65 years.

3.1 Study objectives and outcome measures

To assess the effect of types of plant foods on vascular function in untreated prehypertensive participants.

Primary outcome

Changes in systolic and diastolic blood pressure (mmHg) measured by automated oscillometric device (average of 3 measurements).

Secondary outcomes

Changes (end minus baseline values) in:

1. Arterial stiffness assessed by pulse wave velocity and pulse wave analysis
2. Cardiovascular risk factors measured in fasted plasma samples:

- a. Lipid profiles: total cholesterol, high-density lipoprotein cholesterol, triacylglycerides (low-density lipoprotein cholesterol will be calculated using the Friedewald formula)
- b. Insulin resistance: glucose, insulin, HbA_{1c} (HOMA-IR will be calculated using fasting glucose and insulin values)
3. Markers of endothelial function measured in fasted plasma samples (e.g. C-reactive protein)
4. Markers of low-grade inflammation measured in fasted plasma samples (e.g. Interleukin-6)
5. Urinary and circulatory metabolite profiles and individual metabolite levels
6. Established objective urinary and circulatory markers of food intake:
 - a. Fruits and vegetables: vitamin C, carotenoids, potassium, nitrate
 - b. Salt: sodium
 - c. Protein and muscle mass turnover: urea nitrogen and creatinine
7. Composition of gut microbiota to be measured from stool samples
8. Cognitive function measured by six computerised cognitive tests to assess four main cognitive domains: memory, processing speed, attention, and executive function
9. Self-rated general health and mental well-being
10. Average total, daytime, night time 24-hr ambulatory blood pressure (in subsample)
11. Average objective physical activity intensity and sleep time (in subsample)

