3.3. Study measurements

Participants will be invited to attend the Cambridge Epidemiology & Clinical Trials Unit testing sites for clinical measurements at days 1 and 15 of each intervention sequence having fasted from 10 pm the previous day. Participants will be provided with containers and instructions for urine and stool sample collection. At each clinic visit, participant will bring 24 hour urine and a stool samples that were collected on the previous day, as well as completed food checklists and a questionnaire reporting any medications or dietary supplements used during the specimen collection. The participants will be reminded by text message to complete these collections and questionnaires.

At arrival, a fasting venous blood sample will be taken with a volume that will not exceed 26 ml (156 ml for the whole study: see overview of fractions of blood samples in Table 3). Participants will be asked to void a spot urine for dipstick analyses to check pathological changes in the urine. Automated office BP, pulse wave

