5.1 Outcome definitions

Primary outcomes:

- Systolic blood pressure (mmHg)
- Diastolic blood pressure (mmHg)

Secondary outcomes:

- Pulse wave velocity (m/s)
- Augmentation index (%)
- Total cholesterol (mmol/l)
- HDL cholesterol (mmol/l)
- LDL cholesterol (mmol/l)
- Triglycerides (mmol/l)
- C-reactive protein (mg/L)
- Potassium (mmol/L)
- Sodium (mmol/L)
- Urea nitrogen (mmol/L)
- Creatinine (mmol/L)
- Memory (mm)
- Processing speed (ms)
- Attention (ms)
- Executive function (mm)
- Self-rated general health (score)
- Subjective mood (score)

- Mental well-being (score)

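### SAP 5.1 defines the intake markers potassium, sodium, urea nitrogen and creatinine as mmol/L with no specimen named; if urinary, they are open to dilution bias against control

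*Protocol*

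**What the plan says.** Protocol section 3.1, item 6, gives these analytes a dietary role, under the title "Established objective urinary and circulatory markers of food intake". Its fruit and vegetable line reads "Fruits and vegetables: vitamin C, carotenoids, potassium, nitrate". Sodium is the salt marker, and urea nitrogen and creatinine stand for protein and muscle turnover. Section 2.2 is more specific about specimen: "Established biomarkers to assess fruit and vegetable intakes include urinary potassium and plasma carotenoids".

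On collection, the Study measurements section says that at each clinic visit the "participant will bring 24 hour urine and a stool samples that were collected on the previous day". Table 2 confirms six 24-hour urines, at visits 2 to 7. The spot urine is for dipstick testing only.

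SAP 5.1 lists the outcomes as "Potassium (mmol/L) - Sodium (mmol/L) - Urea nitrogen (mmol/L) - Creatinine (mmol/L"), with no specimen. SAP 5.2 models the end-of-period value of each outcome. It mentions no multiplication by urine volume, no creatinine correction and no completeness check. Neither document says that urine volume is recorded. Vitamin C, carotenoids and nitrate do not appear in SAP 5.1, so potassium is the only fruit and vegetable marker from item 6 that the SAP keeps.

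**The concern.** A timed collection tracks intake because concentration times volume gives the amount excreted over the day. Concentration alone also moves with urine volume, and the two 8-portion diets could plausibly raise volume: they add produce that is mostly water, some of it served as juice or soup, and fluid intake is not fixed by the plan.

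The error would be systematic. SAP 5.2 specifies only each intervention against control, and that is the contrast in which extra water differs. A lower sodium concentration on both active diets could be read as lower salt intake, an obvious rival explanation for a blood pressure difference. A blunted potassium rise could be read as poor adherence. SAP 3.1 promises 95% confidence intervals for all outcomes, so a dilution effect would be reported with an interval that looks like a diet effect.

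**Working it through.** The plan states no figure on this point, so there is none to reproduce. The check is how far dilution alone could move the listed quantities, if they are urinary.

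**From the documents.** Portions per day: 8 on each active diet, 2 on control (Protocol, Dietary intervention). Portion size: 80 g, taken from the recommendation cited in section 2.2; the trial's own portion size is not stated. Extra produce: (8 − 2) × 80 g = 480 g/day.

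**Assumed, not in the documents.** Control urine volume V = 1.2 to 2.0 L/day. Water content about 87.5%, so 480 × 0.875 = 420 g, or 0.42 L/day. Extra urine w = 0 to 0.42 L/day, depending on how far participants drink less.

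**Formulas.** With unchanged excretion, concentration is multiplied by V/(V + w). With a true fractional rise r in excretion, it is multiplied by (1 + r) × V/(V + w). The rise is fully masked only if r ≤ w/V. The middle columns apply these; a 30% rise in potassium is illustrative.

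| V (L) | w (L) | Unchanged excretion reads as | True +30% reads as | Fully masked if rise is at most |
|---|---|---|---|---|
| 1.2 | 0.42 | 1.2/1.62 − 1 = −25.9% | 1.3 × 1.2/1.62 − 1 = −3.7% | 35% |
| 1.5 | 0.42 | 1.5/1.92 − 1 = −21.9% | 1.3 × 1.5/1.92 − 1 = +1.6% | 28% |
| 1.5 | 0.20 | 1.5/1.70 − 1 = −11.8% | 1.3 × 1.5/1.70 − 1 = +14.7% | 13% |
| 2.0 | 0.20 | 2.0/2.20 − 1 = −9.1% | 1.3 × 2.0/2.20 − 1 = +18.2% | 10% |
| any | 0 | 0% | +30% | 0% |

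**Partial offset by drinking less.** With V = 1.5 to 2.0 L and water content 85% to 90%, the fall at unchanged excretion is 5% to 7% if a quarter of the food water reaches urine, 9% to 13% if half does, and 17% to 22% if all does.

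**Potassium from assumed intakes.** Take control excretion of 60 to 80 mmol/day, 3 to 5 mmol per portion and 80% excreted. The true rise is then between 6 × 3 × 0.8/80 = 18% and 6 × 5 × 0.8/60 = 40%. As a concentration it reads +10% to +33%, +3% to +27% and −8% to +16% for the same three shares.

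**What excretion recovers.** Suppose sodium excretion is 140 mmol/day on both diets (illustrative). Concentration reads 140/1.5 = 93.3 mmol/L on control and 140/1.92 = 72.9 mmol/L on an active diet. Multiplying back by volume gives 140 mmol/24 h on both. A ratio of two analytes in the same urine cancels volume as well.

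**The case against.** **The specimen is not established.** Item 6 covers urinary and circulatory markers, and Protocol Table 3 includes serum for biochemistry. A reader might infer that the SAP variables are certainly urinary; the documents do not say so. Urine is the likelier reading, given section 2.2 and the six timed collections, but if serum was meant, urine dilution does not apply. Section 2.2 itself notes that blood levels are homeostatically regulated, so serum values would be weak intake markers. Either way the specimen has to be stated. The unit labels may also be loose: the same list gives memory and executive function in mm.

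**Dilution could be recognised.** "Creatinine (mmol/L") is in the same list and model. Under pure dilution, sodium, urea nitrogen and creatinine fall by the same factor, so a parallel fall would point to water rather than salt. This stands as a partial safeguard, but the SAP does not ask for the outcomes to be read together.

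**Salt has other evidence.** Meals covering 90% of energy are supplied, diets are matched for other food groups, and duplicate diets are analysed. This also stands in part. It does not cover the self-chosen 10% or undeclared extras, and the salt questionnaire is completed only at visits 1 and 7, so it cannot compare periods.

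**The primary result is not biased.** A reader might infer that it is. No urinary analyte enters the blood pressure model, SAP 3.1 gives these secondary outcomes no p-values, and SAP 3.2 analyses adherence from food checklists alone. This objection stands in full. What remains is the interpretation of intake and adherence, for which the protocol does intend to use established biomarkers.

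**Conclusion.** The point holds in conditional form. SAP 5.1 leaves the specimen undefined and uses a quantity that, if urinary, makes poor use of the timed collection.

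On that condition, the active-versus-control contrasts could show a false fall of 0% to 26% at unchanged excretion. The range rests on assumed urine volumes, on an 80 g portion applied to this trial, and on an assumed share of food water reaching urine; it is nil if drinking fully offsets the extra water. Potassium rises would be understated whenever extra water reaches the urine. The stronger reading, that a rise would be hidden, applies only at the extreme: nearly all the water reaching urine together with a low urine volume or a modest true rise.

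The bias largely cancels between the two 8-portion diets. It leaves the blood pressure estimates unchanged and is confined to these four secondary outcomes and what is inferred from them about salt intake and adherence.

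**What to change.** In SAP 5.1, state the specimen for each of the four analytes. For 24-hour urine:

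- If collection volumes were recorded, define the outcomes as excretion, concentration × collection volume, in mmol/24 h. Add a sensitivity analysis that excludes collections flagged as incomplete by 24-hour creatinine, with the flag defined before the data are examined by diet.
- If volumes were not recorded, use a dilution-free ratio: each analyte per creatinine, or sodium to potassium. The latter falls when potassium rises, so it cannot by itself show that salt intake was unchanged.

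If any of the four is a serum value, say so and do not present it as a measure of intake without that caveat.

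The cost is a few lines of SAP text and one multiplication or division per sample. The downsides are that a missed void lowers measured excretion in proportion, hence the completeness check, and that the preferred option depends on recorded volumes.
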